All Veterans enrolled in the study will be beginning a course of either Prolonged Exposure (PE) or Cognitive Processing Therapy (CPT), which will be delivered as usual by PTSD clinical staff. As the BFI is an adjunctive intervention, Veterans' trauma-focused treatment is considered separate from the present study. The Veterans will be seen by regular clinical staff and no artificial limits will be imposed upon their treatment, although treatment engagement will be tracked (see Assessment section, below). Veterans and their family members will be recruited for the present study at the beginning of a course of treatment at the clinic. Phase I will be an open pilot trial of 4 dyads. All family members in Phase I will receive the BFI, which will be delivered as 2 weekly 50-minute sessions of the BFI, consistent with the application with the BFI in previous work (Thompson-Hollands et al., 2015). Phase II will include 20 dyads (N=40) using identical recruitment, inclusion/exclusion criteria, and assessment structure; however, in this second phase family members will be randomly assigned to receive or not receive the BFI, and VABHS clinicians will deliver the BFI sessions (rather than the PI as in Phase I).

Veterans:

Inclusion criteria.

- (1) has a current diagnosis of PTSD

(2) is 18 years of age or older

(3) has an eligible family member (defined as a spouse/significant other, parent, adult child, sibling, etc., 18 years of age or older who currently has substantial daily or weekly contact with the Veteran)

(4) is beginning a course of either CPT or PE at VA Boston.

Exclusion criteria.

(1) has current diagnoses of unstable bipolar disorder, past or present psychosis, or organic mental disorder

(2) has clear and current suicidal risk (assessed via the MINI-Suicide Module (Sheehan et al., 1998), see Assessment section below)

(3) has current moderate or severe substance use disorder

(4) is currently participating in family-based therapy/couples-counseling

Family members:

Inclusion criteria.

(1) is 18 years of age or older

(2) is the family member (defined as a spouse/significant other, parent, adult child, sibling, etc.) of the Veteran

(3) currently has substantial daily or weekly contact with the Veteran

Exclusion criteria.

(1) has a current diagnosis of PTSD

(2) has current diagnoses of unstable bipolar disorder, past or present psychosis, or organic mental disorder

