(2) has clear and current suicidal risk (assessed via the MINI-Suicide Module (Sheehan et al., 1998), see Assessment section below)

(3) has current moderate or severe substance use disorder

(4) is currently participating in family-based therapy/couples-counseling

Recruitment of Veterans and family members will occur through the VABHS outpatient mental health clinics (e.g., the PTSD Clinic, the Women's Clinic, General Mental Health, Center for Returning Veterans, etc.). All interested participants will be contacted by the PI for a phone screen, where the study and its procedures will be described and a short screen for eligibility will be administered. If the initial screening requirements are met, participants will be invited to an in-person assessment. During the first appointment, the Veteran and family member will be provided with a thorough description of the project and the informed consent form will be reviewed and signed. Baseline assessment measures will then be administered (see Assessment section).

Veterans will proceed with PE or CPT as usual through the clinic, with no restrictions or limitations. Should a Veteran choose to discontinue PE or CPT, he or she will continue to be enrolled in the proposed study for follow-up assessments, as treatment drop-out is a variable of interest. All family members who are to receive the BFI (i.e., all family members in *Phase I* and half of family members in *Phase II*) will participate in the two BFI sessions, and then move into the follow-up portion of the study.

BFI: The BFI is a 2-session individual intervention delivered by a clinician to the adult family member of a Veteran with PTSD who is beginning a course of CPT or PE treatment. The BFI sessions are guided by a manual, which has previously been developed by the PI but will

be revised for the purposes of the current study as described earlier to enhance its relevance to the families of Veterans with PTSD. The BFI may be completed either in person or remotely via telephone.

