During the pilot *Phase I* the PI will serve as the BFI clinician. The PI has considerable clinical experience in the treatment of Veterans with PTSD. Additionally, as described above, the PI designed the BFI and has successfully tested its efficacy in a study of patients with OCD and their family members. Beginning in *Phase II* the PI will no longer deliver the intervention; instead, a minimum of 3 clinicians from the VABHS PTSD clinic will be recruited and trained to deliver the BFI.

Comparison condition: Family members in the control or comparison condition of *Phase II* will not receive the BFI or any other study-specific family sessions (aside from the assessments described below). In keeping with the effectiveness aims of the present study, family members in the comparison condition (and the BFI condition) will not be prohibited from receiving any family-inclusive services or sessions that would normally be offered to them in the context of usual VA care.

Independent variables: Receiving or not receiving the BFI (for Veterans/family members); receiving or not receiving training in the BFI (for clinicians).

Dependent variables: Treatment engagement and PTSD symptoms (for patients); accommodation and active treatment support (for family members); qualitative feedback and rates of participation (for Veterans, family members, and clinicians).

Assessment:

Measures and assessment points are shown in Table 1. Qualitative interviews with stakeholders (Veterans, family members, and clinicians) will continue throughout both Phases of the study, as described below. Clinician-rated assessments of Veterans and family members will be completed (in person or via telephone/mail, or a combination of in person and remotely) at baseline and weeks 6, 12, and 16; Veterans and family members will be compensated \$50 for each of these 4 assessment visits that they complete (total of \$200 for the major assessments). Finally, PE and CPT therapists will complete ratings of Veterans' treatment engagement at each session, and will monitor dropout.

Table 1. Assessment Measures and Timepoints

	Time of Administration					
	Baseline	Weeks 0-6	Every PE/CPT session	Week 6	Week 12	Week 16
CAPS-5	X ^v			X ^v	X ^v	X ^v
SCID-5	X ^{v, f}					
Demographics form (Vet/FM)	X ^{v, f}					
Demographics form (Clin)	X ^{tx}					
Relationship information form (Vet)	X ^v					
Relationship information form (FM)	X ^f					
LEC-5	X ^{v, f}					
WTAR	X ^{v, f}					
MOCA	X ^{v, f}					

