Participants will be told the exact nature of the study cannot be revealed to them until completion of the follow-up visits to reduce any bias in the results. Any participant withdrawing early from the experiment will be provided with a debriefing at the time of withdrawal.

This application also involves clinician participants currently working in a VA Boston mental health clinic and regularly providing CPT and/or PE ($n \leq 20$). This part of the proposed study involves: (1) Conducting qualitative interviews with providers regarding family-inclusive PTSD treatment; (2) providing training to providers in the delivery of the BFI; (3) collecting recordings of BFI sessions for the purposes of training and measuring fidelity; and (4) notes and recordings from supervision. Clinicians administering the BFI in Phase II will be asked to complete qualitative interviews at posttreatment and turn in audio recordings of sessions. Data in the form of ratings of digital audio recordings of BFI sessions will be collected from the clinicians to monitor their in-session use of the BFI and assess modifications/adaptations to the protocol. These digital audio recordings will either be hand-delivered to the PI (on the recording device) for her to upload onto a secure research drive, or the recordings will be uploaded to a subfolder on the research drive by the clinicians themselves. Each clinician will have access to a dedicated subfolder on the PI's research drive in which to deposit session recordings; these personal subfolders will also include any training materials or other relevant study information from the PI to the clinician. Clinicians will be therapists who are providers in the VA Boston Healthcare System. Thus they will be over 18, as they will need to have completed their training to become therapists.

b. Sources of research materials

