1. We will carefully screen to identify individuals whose risk for potential adverse outcomes is elevated were they to participate in the proposed research. Such individuals will be excluded from the study. As an

example, an actively suicidal person would be excluded from study participation and appropriate clinical treatment or referrals provided.

2. Clinical staff will be trained to cope with any anxiety/distress experienced by participants during the assessments and intervention. Staff will also monitor assessment items that ask about risk of suicide or current domestic violence at each timepoint. These items will be reviewed immediately upon completion, and participants who endorse elevated risk of suicide or current domestic violence will meet with the PI for further assessment. See Section 5b ("Safety monitoring plan") below for details of the standard procedure for suicidal risk. For current domestic violence, the PI (in consultation with a licensed clinical supervisor on site) will assess risk and provide the participant with clinical and community referrals as needed.

3. Careful monitoring of participants during study participation will be conducted by the project staff. Participants will be monitored for any increase in symptoms as the study progresses. Each participant will see the same clinician for each of their treatment or intervention visits (in the case of Veterans, their same usual care clinician. In the case of family members, the same BFI clinician), and the same assessor for each assessment occasion when appropriate. Following the clinical trial policy of the VA Boston Healthcare System, all participants will be given an emergency number to call in case of an emergency. This number will be the psychiatry on call system of the VA Boston Healthcare System.

4. Participants will be instructed to contact study personnel at any time (including during the follow-up period) in the event of worsening symptoms. Participants whose clinical condition has deteriorated will be removed from the study and given appropriate clinical care. See DSMP for details.

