Hypothesis 2a-2c analytic strategy: Multilevel regression (i.e., hierarchical linear modeling (HLM), growth curve analysis, etc.) will be used to evaluate change in continuous outcome variables (Singer & Willett, 2003). Multilevel regression is a robust method for analyzing change over time, with excellent options for handling missing data, powerful estimation abilities, and flexibility of modeling. This approach will allow for the analysis of an intent-to-treat sample in line with CONSORT guidelines (Altman et al., 2001). For our analysis of change in the variables of interest we will use a multilevel framework in the Mplus program to model time as a Level 1 predictor of the outcome variables (baseline and weeks 6, 12, and 16). We will first specify an unconditional model to ascertain the shape of the change trajectories (e.g., linear versus quadratic change over Time), and will subsequently specify conditional multilevel models to examine treatment effects and the impact of other variables as predictors of individual differences in change. We will also calculate the Cohen's *d* effect size and 95% confidence intervals in order to provide a benchmark for future trials.

o. Literature Cited

Aarons, G. A., Cafri, G., Lugo, L., & Sawitzky, A. (2010). Expanding the domains of attitudes towards evidence-based practice: The Evidence Based Practice Attitude Scale-50. *Administration and Policy in Mental Health and Mental Health Services Research*, 39(5), 331–340. <http://doi.org/10.1007/s10488-010-0302-3>

Boeding, S. E., Paprocki, C. M., Baucom, D. H., Abramowitz, J. S., Wheaton, M. G., Fabricant, L. E., & Fischer, M. S. (2013). Let me check that for you: symptom accommodation in romantic partners of adults with Obsessive-Compulsive Disorder. *Behaviour Research and Therapy*, 51(6), 316–322. <http://doi.org/10.1016/j.brat.2013.03.002>

Borkovec, T.D., & Nau, S.D. (1972). Credibility of analogue therapy rationales. *Journal of Behavior Therapy and Experimental Psychiatry*, 3, 257-260.

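### If outcomes vary by BFI clinician, the H2a/H2b p-values and the Cohen's d interval may overstate precision, because as few as 3 clinicians may treat all 10 Phase II BFI families and neither the model nor a caseload rule allows for it

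*Combined protocol and SAP*

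**What the plan says.** **Numbers and delivery.** Section (4) Work Proposed states: "Phase II will include 20 dyads (N=40) using identical recruitment, inclusion/exclusion criteria, and assessment structure". The same section gives the BFI to half of the Phase II family members, and the developer stops delivering it at that point. Instead, "a minimum of 3 clinicians from the VABHS PTSD clinic will be recruited and trained to deliver the BFI". Three is a floor. No maximum, target or even caseload is stated. Family members in the comparison condition get no study family sessions.

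**Continuity.** Section 2.b (Protection against risk), item 3, keeps each participant with one clinician across visits: "In the case of family members, the same BFI clinician".

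**Analysis.** The analytic strategy for Hypotheses 2a-2c uses a "multilevel framework in the Mplus program to model time as a Level 1 predictor of the outcome variables". Conditional models then add treatment and other person-level predictors of change. No clinician level, cluster-robust standard error, ICC or design effect appears. The same paragraph promises Cohen's d with a 95% confidence interval as a reference value for later trials, and the analysis overview tests all quantitative outcomes at two-sided .05. Both power sections call the study preliminary and give no figures.

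**The concern.** This is a partially nested design. BFI dyads are grouped by the clinician who delivers the BFI; control dyads have no such grouping. If some clinicians obtain better results than others, families sharing a clinician resemble one another. The BFI-arm mean is then more variable than 10 independent dyads would make it, while the spread seen within the arm shrinks slightly. A model without a clinician term registers neither.

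At stake are the tests of H2a and H2b and the interval for d. The trial is presented as an effectiveness study in which clinic staff replace the developer, so a later user will want to know how the BFI performs with VA clinicians in general. An interval that covers only these few clinicians, without saying so, could be read as answering that question.

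**Working it through.** The plan states no power, detectable effect or ICC, so there is no figure of its own to reproduce.

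**Inputs from the documents.** 20 Phase II dyads, half to the BFI: 20 × 0.5 = 10 against 10. At least 3 clinicians: 10/3 = 3.3 families each at the minimum. One BFI clinician per family, none for controls. Two-sided alpha .05.

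**Assumed.** Clinician ICC of 0.05, 0.10 or 0.20. Caseloads of 4/3/3 (as even as 3 clinicians allow), 8/1/1 (lopsided but permitted) and 2/2/2/2/2 (five clinicians). Total variance 1 in each arm, no true effect, and a pooled two-sample t-test on 18 df standing in for the four-timepoint growth model.

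**Step 1, effective caseload.** m = Σ(caseload²)/10.
- 4/3/3: (16 + 9 + 9)/10 = 3.4
- 8/1/1: (64 + 1 + 1)/10 = 6.6
- 2 × 5: 20/10 = 2.0

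**Step 2, design effect, BFI arm only.** DE = 1 + (m − 1) × ICC.
- 4/3/3: 1.12, 1.24, 1.48
- 8/1/1: 1.28, 1.56, 2.12
- 2 × 5: 1.05, 1.10, 1.20

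**Step 3, true SE over reported SE.** The variance of the difference in means rises by (DE + 1)/2. The pooled variance the analyst computes falls, on average, to 1 − 0.5 × ICC × (m − 1)/9. So

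R = √[(DE + 1)/2] / √[1 − 0.5 × ICC × (m − 1)/9].

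Example, 4/3/3 at ICC 0.20: √1.24 / √(1 − 0.5 × 0.20 × 2.4/9) = 1.1136/0.9866 = 1.13.

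**Step 4, width of the d interval.** Near d = 0 the plain half-width is 1.96 × √(2/10) = 1.96 × 0.447 = 0.877. Multiply by R.

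**Step 5, type I error.** Simulated with 200,000 replicates per case; repeat runs agree to about 0.2 percentage points.

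| Caseload | ICC | R | d half-width | Type I error |
|---|---|---|---|---|
| any | 0 | 1.00 | 0.88 | 5.0% |
| 4/3/3 | 0.05 | 1.03 | 0.91 | 5.7% |
| 4/3/3 | 0.10 | 1.07 | 0.93 | 6.3% |
| 4/3/3 | 0.20 | 1.13 | 0.99 | 7.9% |
| 8/1/1 | 0.05 | 1.08 | 0.94 | 6.7% |
| 8/1/1 | 0.10 | 1.15 | 1.01 | 8.5% |
| 8/1/1 | 0.20 | 1.29 | 1.13 | 12.0% |
| 2 × 5 | 0.05 | 1.01 | 0.89 | 5.3% |
| 2 × 5 | 0.10 | 1.03 | 0.90 | 5.6% |
| 2 × 5 | 0.20 | 1.05 | 0.92 | 6.1% |

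**Step 6, can a clinician variance be estimated?** With 4/3/3, the ANOVA estimate of clinician variance is zero or negative in about 53% of simulated trials at ICC 0.05 and about 40% at ICC 0.20. A random effect would often collapse to the plain model.

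**The case against.** **No ICC is given.** A reader might infer that the standard errors are definitely too small. The documents do not support that: it holds only if the clinician ICC is above 0, and at ICC 0 nothing changes. This stands.

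**The ordinary case is mild.** With even caseloads and ICC 0.05 to 0.10, the standard error moves by 3 to 7%. Ten dyads per arm already give an interval of about ±0.88, so small numbers dominate the imprecision, and the plan calls itself preliminary. This stands, and it sets the weight of the point.

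**The large figures stack assumptions.** The 12.0% needs minimum staffing, a lopsided caseload and ICC 0.20 together. Nothing suggests that such a caseload is intended, and three is a floor. True; but nothing prevents it either.

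**Delivery is controlled.** The BFI is two manual-guided sessions, all recorded, with independent quality checks, adherence ratings, supervision and retraining for drift. This weighs against the higher ICCs but does not correct a standard error.

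**H2a is remote.** The BFI clinician never treats the Veteran, so an effect on CAPS-5, homework or attendance would be indirect. A clinician effect is likelier for H2b, where the clinician works directly on accommodation and support. This stands. Grouping by the Veteran's PE or CPT therapist can occur in both arms and is a separate matter.

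**Being a pilot does not dispose of it.** The plan still tests at .05 and offers the d interval for use by later trials, so its scope should be stated.

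**Conclusion.** The structure is as described: 10 BFI families, possibly 3 clinicians, no caseload rule, and no clinician term in the stated model. The consequence is conditional. If outcomes vary by BFI clinician, the p-values and the d interval may overstate precision: modestly with even caseloads, more with lopsided ones, little with five or more clinicians, and not at all at ICC 0. These sizes rest on assumed ICCs and on a single-endpoint t-test, so they are approximations to the planned growth model.

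A reader might also infer that the primary model must carry a clinician random effect. The plan's own numbers do not support that, since about 3 clusters in one arm cannot give a reliable variance estimate. For the same reason, this trial cannot supply a usable ICC for the later study. This is a cheap improvement, not a flaw that undermines the trial.

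**What to change.** 1. Assign BFI families to the trained clinicians in rotation, so that caseloads are as equal as possible (4/3/3 with three clinicians). At ICC 0.20 this alone lowers the worst illustrated type I error from 12.0% to 7.9%.
2. Hold the BFI clinician's identifier for each dyad in the analysis data, and report families per clinician. Session recordings already go into a separate folder for each clinician or to the investigator, so this should be easy to recover.
3. Keep the planned model as primary. Label its Cohen's d interval as conditional on these clinicians. Beside it, report intervals and p-values for H2a and H2b with the standard error multiplied by R, computed from the actual caseloads at ICC 0.05, 0.10 and 0.20. State that the ICCs are assumed.
4. Do not make a clinician random effect the primary model.

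Cost: SAP wording, one identifier field and a rotation rule, with no extra participants or staff. The downside is wider sensitivity intervals and a small scheduling constraint. If BFI delivery has finished, items 2 and 3 can still be done.

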The Beck Anxiety Inventory (BAI) (Beck et al., 1988)

The Inventory of Psychosocial Functioning (IPF-80) (Bovin et al., 2018) will be used to index objective role functioning/impairment in the following domains: romantic relationship, family, parenting, work, friendships and socializing, education, and self-care

PTSD Checklist-5 (PCL-5) (Weathers, Litz, Huska, & Keane, 1994)

Revised Conflict Tactics Scale (CTS-2) (Straus, Hamby, Boney-McCoy, & Sugarman, 1996)

Posttraumatic Avoidance Behavior Questionnaire (PABQ) (van Minnen & Hagenaars, 2010)

Posttraumatic Cognitions Inventory (PTCI) (Foa, Ehlers, Clark, Tolin, & Orsillo, 1999)

At each PE or CPT session, the Veteran's therapist will complete (1) a record of session attendance (or dropout, if applicable), along with (2) the Homework Compliance Scale (Leung & Heimberg, 1996) (HCS).

Family member-specific assessments:

Family members will complete/be assessed using the following previously described measures, as outlined in Table 1:

SCID-IV

Demographics form

Relationship information form

AUDIT

LEC-5

WTAR

MOCA

MINI-Suicide module (only administered at follow-up if score was ≥ 1 at baseline, see DSMB section)

RDAS

PCS

MSPSS

DERS

BDI-II

BAI

IPF-80

CTS-2-SF

PCL-5 (family members will rate the PCL-5 based on their perception of the Veteran's current symptoms)

Family members will also complete the following (timing outlined in Table 1):

Significant Others' Responses to Trauma Scale (Fredman et al., 2014) (SORTS)

Caregiving Appraisal Scale (Lawton, Moss, Hoffman, & Perkinson, 2000)

Involvement in Therapy Checklist (ITC). This measure consists of a checklist of involvement in the Veteran's treatment since the last assessment (assisting with therapy homework, driving patient to appointments, attending therapy sessions with the Veteran, etc.).

Treatment Expectancy Questionnaire (TEQ; Borkovec & Nau, 1972). The TEQ will be administered immediately after the first BFI session. Wording was modified slightly to better describe the family program.

The therapeutic alliance following the BFI will be assessed using the 12-item therapist and client versions of the Working Alliance Inventory (WAI; Horvath & Greenberg, 1989; Tracey & Kokotovic, 1989). Wording was modified slightly to better describe the family program.

The Client Satisfaction questionnaire (CSQ) will assess family members' satisfaction with the overall program.

Clinician-specific assessments:

Demographics form

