The codes that link the names of participants and their ID numbers will be kept confidential by the PI in a secured cabinet located within the PI's office (JP campus, room 13B-60) (or, during construction on the 13th floor of Building 1 in JP, in a secure basement storage area appropriate for materials containing PII). Collected data forms will be in a locked file cabinet located in the PI's office (or, during construction on the 13th floor of Building 1 in JP, in a secure basement storage area appropriate for materials containing PII). These data are accessible to the PI and personnel working on the project. Data will be entered electronically by trained staff, and data entry discrepancies will be corrected by the data entry supervisor based on source documents. The quality of the data will be monitored quarterly. Data will be securely transmitted using VA approved methods.

Audio recordings will be captured using Philips recorders with FIPS 140-2 validated encryption. Recordings may be obtained while study staff are teleworking; in these cases the recorders will be stored in the home in a locked cabinet/drawer that is only accessible to the study staff member. Recorders will be hand-carried to the VA as soon as it is feasible and safe to do so, at which point the recordings will be uploaded to the PI's personal research drive behind the VA firewall and deleted from the recording device.

The primary outcomes measures will be CAPS-5 total scores and ratings of homework completion (from the Homework Completion Scale), and number of sessions attended/dropout. Data quality will be monitored by inspection of the completed forms by the research assistant and any problems detected will be discussed with the PI. All assessors will be fully trained on the assessment measures, per the usual training procedures within BSD. Adherence to the intervention will be monitored using recordings of sessions and weekly supervision, as described previously. If diagnostic and/or intervention drift is observed, staff will be retrained until acceptable reliability is reached.

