Power analyses: Determining sample sizes for multilevel models is a complex issue and "rules of thumb" are disputed (Maas & Hox, 2005; Mok, 1995). Furthermore, "effective" sample sizes in MLMs (as opposed to nominal sample sizes) will vary according to the model's predictors (Bickel, 2007). Given the aims and scope of this funding mechanism, the present study is considered preliminary. It will provide pilot data to assess the effectiveness of the BFI as well as exploring the proposed mechanisms of action. The use of repeated measures increases our ability to detect significant relationships. Our results will inform next steps in the investigation of the effectiveness and implementation of the BFI, including a fully powered R01 application to examine the BFI in comparison to an established family-based treatment in a routine VA clinic.

Defining key concepts for analyses:

Treatment dropout: Consistent with past trials of CPT and PE, treatment dropout will be defined by ending treatment prior to the allocated treatment period. In the case of CPT full treatment duration is 12 sessions, while in the case of PE full treatment duration is at least 8 sessions and the concomitant agreement of the therapist that an appropriate ending place has been reached. Any Veteran who ends treatment prior to these milestones will be considered a dropout.

Feasibility/Acceptability: In the current study, feasibility and acceptability will refer to the evaluation and analysis of recruitment, randomization, retention, treatment adherence and fidelity, and use of the BFI with the families of Veterans beginning PTSD treatment. These variables help to determine the acceptability of the treatment and procedures for future studies.

Aim 1: Collect qualitative and quantitative data on feasibility and acceptability of the BFI in a routine care setting.

Hypothesis 1: Levels of feasibility and acceptability of the BFI among Veterans, family members, and clinicians will be high and comparable to levels found in the previous efficacy trial in OCD.

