Hypothesis 1 analytic strategy: We will examine the feasibility and acceptability of the BFI by examining rates of BFI recruitment and refusal, as well as level of drop-out from the BFI sessions. These data will be benchmarked to previous BFI efficacy data. We will also assess the success of the clinician training program by reviewing rates of clinician recruitment and attitudes reported on the EBPAS-50. Furthermore, we will conduct detailed in-person, semi-structured exit interviews with Veterans, family members, and clinicians in order to collect qualitative data. These data will allow us to contextualize our findings related to the protocol's fit in this novel setting and its acceptability to Veterans, families, and providers. The qualitative interviews will provide more nuanced feedback regarding the perceived fit of the BFI, and further identify necessary modifications to the protocol (see below for qualitative analytic strategy).

Aim 2: Assess the BFI's effects on symptoms as well as potential mechanisms of change using multilevel modeling.

Hypothesis 2a: Veterans whose family members receive the BFI will show lower levels of PTSD symptoms at post-treatment and greater engagement throughout treatment compared to control Veterans.

Hypothesis 2b: Family members who receive the BFI will show more active support for treatment and less accommodation than control family members.

Hypothesis 2c: Family members' active support for treatment will be positively related to Veterans' treatment engagement, and Veterans' levels of perceived criticism will be negatively related to their treatment engagement

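### Primary attendance outcome is a raw session count although PE and CPT courses differ in length, so it misorders Veterans; separately, homework is compared only among sessions attended

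*Combined protocol and SAP*

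**What the plan says.** The Data Monitoring Plan (section 5a) names the primary outcomes: "The primary outcomes measures will be CAPS-5 total scores and ratings of homework completion (from the Homework Completion Scale), and number of sessions attended/dropout". Hypothesis 2a predicts "greater engagement throughout treatment compared to control Veterans".

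Under Assessment, the treating therapist "will complete (1) a record of session attendance (or dropout, if applicable), along with (2) the Homework Compliance Scale" at every PE or CPT session. Table 1 lists homework only in the per-session column, not at weeks 6, 12 or 16. (The scale is called Compliance in one place and Completion in the other; the names should be reconciled.)

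Course length is set out under Treatment dropout in the Data Analysis section: "In the case of CPT full treatment duration is 12 sessions, while in the case of PE full treatment duration is at least 8 sessions", with the therapist's agreement also needed for PE. The same paragraph adds: "Any Veteran who ends treatment prior to these milestones will be considered a dropout". The Work Proposed section places no limit on the Veteran's therapy. No section gives the session count a denominator, says how session ratings become a score per Veteran, or says what a missed or post-dropout session contributes to homework.

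**The concern.** A count means the same thing for two Veterans only if their courses are equally long. Here they are not, and there is no upper limit. The count can therefore place someone who finished treatment below someone the plan itself calls a dropout, and a Veteran whose therapy is extended scores as more engaged than one who finished on time. With 20 randomised dyads, a chance difference in PE/CPT mix between arms can also move the mean count by about as much as a real retention effect.

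Homework raises a different question. Ratings exist only while the Veteran attends, and the BFI is meant to keep in therapy Veterans who would otherwise leave. If those Veterans do less homework, holding on to them changes whose homework is averaged. After a Veteran leaves therapy there is no homework to observe, so this is not an ordinary missing value that a multilevel model recovers.

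At stake is the engagement signal that the pilot hands on to the larger trial it is meant to inform.

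**Working it through.** The plan states no engagement figure, so there is nothing to reproduce. From the documents: CPT course 12 sessions, PE at least 8, dropout up to 36% (Rationale), 20 randomised dyads with half receiving the BFI. Everything else below is assumed for illustration.

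**Ordering.** A PE completer at 8 sessions counts 8. CPT Veterans who leave after 9, 10 or 11 sessions are dropouts by the plan's definition and count 9 to 11. This needs no further assumption.

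**Effect of PE/CPT mix on the count.** Assume PE completers attend 8 sessions, CPT completers 12 and dropouts 4, with dropout 18% (BFI) v 36% (control). Mean sessions = (1 - d) × [p × 8 + (1 - p) × 12] + d × 4, where d is dropout and p the PE share.
- Equal mix (p = 0.5 in both arms): 0.82 × 10 + 0.72 = 8.92 v 0.64 × 10 + 1.44 = 7.84, so +1.08 for the BFI.
- PE share 70% BFI, 30% control: 0.82 × 9.2 + 0.72 = 8.26 v 0.64 × 10.8 + 1.44 = 8.35, so -0.09. The benefit disappears.
- Same mix, dropout 36% in both arms: 0.64 × 9.2 + 1.44 = 7.33 v 8.35, so -1.02 with no effect at all.
- Mix reversed (30% BFI, 70% control), dropout halved: 0.82 × 10.8 + 0.72 = 9.58 v 0.64 × 9.2 + 1.44 = 7.33, so +2.25. The benefit is exaggerated.
- PE completers at 9 instead of 8, mix 70% v 30%, dropout halved: 0.82 × 9.9 + 0.72 = 8.84 v 0.64 × 11.1 + 1.44 = 8.54, so +0.29. The benefit shrinks but survives.

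How likely is such a mix? If 10 of the 20 Veterans are in PE and arms are 10 v 10, the chance of a 7:3 split or worse in either direction is 2 × (C(10,3)² + C(10,2)² + C(10,1)² + 1) / C(20,10) = 2 × 16,526 / 184,756 = 0.179.

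**The same case on a proportion.** Score completers 1 and dropouts at 4 sessions 4/8 = 0.50 (PE) or 4/12 = 0.33 (CPT). With the 70% v 30% mix and halved dropout:
- BFI: 0.82 + 0.18 × (0.7 × 0.50 + 0.3 × 0.33) = 0.90.
- Control: 0.64 + 0.36 × (0.3 × 0.50 + 0.7 × 0.33) = 0.78.

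The retention benefit is visible again.

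**Homework.** Assume a 0-6 scale, 64% of Veterans scoring 5 over 12 sessions, and 36% scoring 2. In control all of the latter leave after 3 sessions; with the BFI half of them stay for 12. Nobody's homework changes.
- All sessions pooled: control (0.64×12×5 + 0.36×3×2) / (0.64×12 + 0.36×3) = 40.56/8.76 = 4.63; BFI 43.80/10.38 = 4.22; difference -0.41.
- Completers only: 5.00 v (0.64×5 + 0.18×2)/0.82 = 4.34; difference -0.66.
- Equal-weight mean per Veteran: 0.64×5 + 0.36×2 = 3.92 in both arms; difference 0.
- Random intercept per Veteran, weight n/(n + r) for n sessions, where r is residual over between-Veteran variance: -0.04, -0.07, -0.12 and -0.16 for r = 0.5, 1, 2 and 3.
- Per planned session, unattended sessions scored 0: 40.56/12 = 3.38 v 43.80/12 = 3.65; difference +0.27.

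If instead homework is 4.5 (engaged) or 2.5 (less engaged) and the latter falls by 0.1 per session, the equal-weight mean per Veteran differs by -0.05 to -0.08 for dropout after 6 to 3 sessions.

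**The case against.** Four points on the other side have force.

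1. **Retention does not lower the count.** A reader might infer that keeping Veterans in therapy costs the BFI on attendance. It does not: in the homework example the mean count rises from 8.76 to 10.38 sessions. The fault lies in unequal and uncapped course lengths.
2. **Dropout is also measured.** It is scored against therapy-specific milestones, and the Missing data paragraph commits to reporting its rate and exact timing. Retention is therefore credited directly, and the documents do not support inferring that the trial would conclude that the BFI harms engagement. This does not repair the count, and no rule says how to read the two if they disagree.
3. **A PE/CPT imbalance is chance noise, not bias.** It works in either direction, and the analysis overview says unbalanced factors will be controlled for. That stands in part: therapy type is not named as such a factor, no criterion for imbalance is given, and adjustment alone would still reward prolonged treatment within a therapy.
4. **The planned analysis is multilevel, not pooled.** The -0.41 sign reversal is tempting to quote as the homework result, but a model with Veteran-level effects removes most of it. What remains is that the stated time points (baseline, weeks 6, 12 and 16) do not fit ratings made at each session, and the summary per Veteran is unspecified.

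It is also fair that homework quality while in therapy is a legitimate outcome in its own right. The need is to label it as conditional, not to replace it.

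**Conclusion.** The attendance point holds. The misordering of PE completers and CPT dropouts follows from the plan's own definitions. Its effect on the arm comparison depends on the mix that chance delivers: on the assumed inputs, halved dropout can show as anything from -0.09 to +2.25 sessions, against +1.08 with equal mix. The distortion shrinks as PE courses approach 12 sessions.

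The homework point holds in a modest form. The comparison is conditional on retention, and the bias against the BFI is about 0 to -0.16 points under a per-Veteran mean or a random-intercept model. It becomes large only if sessions are pooled (-0.41) or completers alone are analysed (-0.66), neither of which the plan proposes. The scale range, homework levels, 18% BFI dropout, session numbers at dropout and PE/CPT mixes are all assumptions.

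This is a small pilot, so no single engagement comparison will be decisive. The definitions are still worth settling before analysis.

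**What to change.** 1. **Attendance.** Analyse the proportion of the therapy-specific full course attended, capped at 1, with the milestones in the Treatment dropout paragraph as denominators (12 for CPT, 8 for PE). A Veteran who ends by the plan's completion definition scores 1. Include therapy type (PE/CPT) as a covariate and report dropout beside it. Dropout is needed there because a PE Veteran who stops at 8 or more sessions without the therapist's agreement also scores 1 but is a dropout.
2. **Homework.** State that the rating at attended sessions is a conditional measure. Summarise it per Veteran, or fit a Veteran-level random-intercept model on a per-session time scale; do not pool sessions.
3. **Sensitivity analysis.** Add mean homework per planned session over the same denominator, with missed and post-dropout sessions scored as no homework. Use a mean, not a sum, because a sum would bring course length back in.

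The cost is a few lines of outcome definition; therapists already record attendance and dropout at each session. There are two downsides. Capping ignores sessions beyond the milestone. The sensitivity score mixes retention with homework quality: in the example it shows +0.27 although nobody's homework changed. It should therefore stand beside the conditional measure and not replace it.
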